2.3 Use of radiation: N/A

2.4 Use of Center for Magnetic Resonance Research:N/A

3.0 Provisions to Monitor the Data to Ensure the Safety of Participants

3.1 Protecting Privacy: Subjects are working with physical therapy regardless of enrollment in this study. At any time they can request to stop either therapy or the study. Their medical records are secured in the Fairview system. Data extracted for study purposes is accessed by the primary therapist and de-identified prior to input into REDcap system.

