16.5 Adults Unable to Consent: N/A

17.0 Setting

17.1 Research Sites: Fairview, University of Minnesota Medical Center, East Bank Hospital. Treatment and consent will occur in the hospital room of each subject.

18.0 Multi-Site Research:

N/A

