 - Richmond Agitation and Sedation Scale (RASS), as completed in medical record by primary nurse
 - Functional Status Score for the Intensive Care Unit (FSS-ICU)
- Hospital Outcomes (data extraction from medical record)
 - Hospital days
 - Intensive care unit days
 - Days on ECMO
 - Days on mechanical ventilation
 - Length of time from physical therapy evaluation to initial ambulation
 - Discharge disposition- assigned a number for statistical analysis
 - Home (1)
 - Home with assistance (2)
 - Home with home therapy (3)
 - Home with outpatient therapy (4)
 - Transitional Care Unit (5)
 - Acute Inpatient Rehabilitation (6)
 - Long-term acute care hospital (7)
 - Long-term care setting (8)
 - Transfer to outside hospital (9)
- Physiological Monitoring: Monitoring physical therapists have extensive experience in mobilizing patients in the ICU, including those with arterial lines and on ventilation, as is standard practice for ICU therapy.
 - Respiratory rate (RR) via Drager Ventilators
 - Evita Series or Infinity Series
 - Oxygen (SpO2) and heart rate (HR)
 - Spacelabs Ultraview SL2700 (regular monitor)
 - Spacelabs Ultraview SL (portable monitor)
 - Blood Pressure (BP) via manual cuff or arterial line
 - Spacelabs Ultraview SL2700 or SL

Statistical Considerations

Physiological data (HR, BP, O2, RR) will be recorded throughout the study and analyzed between Groups A and B. Functional and Hospital outcomes will be analyzed to compare group differences at each of the data collection days (0, 5, 10, 15, 20, 30, 45, day of discharge).

Data will be analyzed at the University of Minnesota using the Statistical Package for Social Sciences (SPSS) software program. Test for normality will be completed via a paired t-test for parametric data and via Wilcoxon Rank Sum Test for non-parametric data.

Aim 1: Leg exercise on the Moveo will decrease time to initial ambulation.

- A paired t-test will be used to evaluate time to ambulation in Group A as compared to Group B.

Aim 2: Leg exercise on the Moveo will improve functional outcomes.

- There are 2 primary factors to assess, Group A and B, as well as the impact across time. To assess both factors, repeated measures ANOVA will be used.

Aim 3: Leg exercise on the Moveo will improve hospital outcomes.

- All hospital outcomes, except for discharge disposition, can be assessed between Group A and Group B by a paired t-test.
- Discharge disposition, categorical data, will be analyzed via Chi-Square test.

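### Ventilator and ICU days appear to stop at transfer, so a patient who leaves still receiving that care is compared as a short, finished count; Aim 3 has no rule for this

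*Combined protocol and SAP*

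**What the plan says.** The list of hospital outcomes in the project proposal is introduced as "Hospital Outcomes (data extraction from medical record". It includes hospital, ICU and ECMO days and "Days on mechanical ventilation". The same list has "Discharge disposition- assigned a number for statistical analysis", whose nine levels include "Long-term acute care hospital (7" and "Transfer to outside hospital (9" beside the home and rehabilitation levels. Death is not a level.

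On the source of the data, section 3.1 says of participants: "Their medical records are secured in the Fairview system". Section 17.1 names one site, "Fairview, University of Minnesota Medical Center, East Bank Hospital", and section 18.0 marks multi-site research as not applicable. Under Data Collection for Aims 1-3, discharge is the last point at which data are taken.

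On analysis, Statistical Considerations says under Aim 3: "All hospital outcomes, except for discharge disposition, can be assessed between Group A and Group B by a paired t-test". Disposition has its own chi-square test. The same section says hospital outcomes are compared at every scheduled collection point, of which discharge is one. It names the Wilcoxon rank-sum test for non-parametric data. Nothing links the day counts to disposition, and no section defines the end of a count, sets a fixed horizon or provides for data from a receiving facility.

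**The concern.** For the day counts, the Aim 3 hypothesis of improvement means fewer days. If counting stops when the patient leaves the building, a patient who moves elsewhere still on a ventilator, or still needing ICU care, contributes fewer days than a patient with the same course who stays. Unfinished care is then scored in the favourable direction, and the arm with more such patients looks better for a reason unrelated to the exercise. With about 10 patients per arm, one or two patients can move the mean visibly.

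The problem is sharpest for ventilator and ICU days, because the outcome is the duration of a specific type of care and that care is known to be continuing. Hospital days are less clear-cut, since days in the study hospital are a meaningful quantity in their own right.

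**Working it through.** **Does the count stop at transfer?** Four features, read together:

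1. The day counts come from the medical record (Hospital Outcomes).
2. The only record described is the Fairview one, at one site (sections 3.1, 17.1 and 18.0).
3. Collection ends at discharge (Data Collection for Aims 1-3).
4. Codes 7 and 9 are levels of discharge.

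It follows that nothing is counted after a transfer. This is an inference. No sentence states it, and none contradicts it.

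**Inputs.** The plan has no figure on this point to reproduce. Its only relevant number is the sample size: 10 per group, raised to 12 for attrition, and 2 x 12 = 24. Transfer counts, unobserved days and SDs below are assumptions.

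**Size of the bias.** Let kA and kB be the numbers in each arm who leave with the care continuing, n the arm size, and L the unobserved days per such patient. With identical true durations in both arms:

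spurious mean difference = (kA - kB) / n x L

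For n = 10:

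| Transfers, A vs B | L = 7 | L = 14 | L = 30 |
|---|---|---|---|
| 1 vs 0 | 1/10 x 7 = 0.7 | 1/10 x 14 = 1.4 | 1/10 x 30 = 3.0 |
| 3 vs 1 | 2/10 x 7 = 1.4 | 2/10 x 14 = 2.8 | 2/10 x 30 = 6.0 |
| 2 vs 2 | 0 | 0 | 0 |

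With 12 per arm, the 1 vs 0 row becomes 0.58, 1.17 and 2.5 days. On a standardised scale, the largest entry, 6.0 days, is 6.0/25 = 0.24, 6.0/20 = 0.30 or 6.0/15 = 0.40 SD for assumed SDs of 25, 20 and 15 days.

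**Effect on the test.** An illustrative simulation used 40,000 runs, 10 per arm, identical lognormal stays (assumed mean 45, SD 25 days), the longest stays transferred, and a two-sided 5% independent-samples t-test because the arms are independent. Rates of false significance in favour of the arm listed first:

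| Transfers | L = 7 | L = 14 | L = 30 |
|---|---|---|---|
| none | about 2.3% | about 2.3% | about 2.3% |
| 1 vs 0 | 3.0% | 3.6% | 5.7% |
| 3 vs 1 | 4.5% | 7.6% | 18.4% |
| 2 vs 2 | 3.5% | 5.0% | 7.8% |

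The 2 vs 2 row has no mean bias. Its rates rise because always shortening the longest stays shrinks the within-arm spread. Part of the inflation in the other rows has that source too, so 18.4% is an upper-end illustration.

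**Does the disposition test protect?** Nine levels by two arms is 18 cells, and 20 patients give 20/18 = 1.1 per cell on average. Even collapsed to transferred or not, 3 vs 1 out of 10 gives Fisher p = 0.58 and 4 vs 1 gives p = 0.30. The table would show the imbalance, but the test would rarely flag it, and neither alters the day counts.

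**The case against.** The strongest reply is that days in the index hospital are a coherent outcome for a single-site pilot in which patients take part for as long as they are hospitalised there. That stands for hospital days, and is why they should remain the main comparison under an accurate label. It does not carry over to ventilator and ICU days in a patient whose care is known to be unfinished.

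Three stronger readings are tempting and are not supported:

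- A reader might infer that the plan makes a disposition code end the count. It does not. The codes are only levels of an outcome. If anything ends the count it is discharge itself, which applies to every code.
- A reader might infer that every patient coded 7 or 9 had a poor outcome. The reason for transfer is not recorded, and ICU care may truly have ended before a move to long-term acute care.
- A reader might infer that the Aim 3 result is likely to point the wrong way. That needs an imbalance between arms and a long gap, and the documents give neither.

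It is also fair to say that totals at discharge are only one of the scheduled comparisons, and that disposition is reported by arm, so an imbalance would be visible. But the plan does not say how a transferred patient enters the comparisons on later fixed days, and visibility is not correction.

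Ranking all transfers as worst for hospital days would go too far. If deaths kept their recorded days, an early death would rank better than a transfer.

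**Conclusion.** The point holds for ventilator and ICU days in patients who leave with that care continuing: their counts are incomplete but are compared as complete, in the direction the hypothesis favours. It rests on the inference that counting ends at discharge from the study hospital.

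The size is uncertain: 0.7 to 3.0 days for one extra transfer among 10 per arm over assumed gaps of 7 to 30 days, more with a larger imbalance, and zero when transfers and unobserved days balance. This concerns the third aim of a pilot, so it is a worthwhile and inexpensive improvement and no threat to the study as a whole. For hospital days, labelling and a sensitivity analysis are enough.

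**What to change.** 1. State in the plan when each day count ends.
2. Record at discharge whether the patient is still ventilated and whether the patient is still in ICU. Record in-hospital death as well, since the disposition list has no level for it.
3. For ventilator and ICU days, treat patients who leave with that care continuing as not completed. Compare the arms by the Wilcoxon rank-sum test, with these patients and in-hospital deaths ranked together above the longest completed count. Show days as recorded alongside. Patients coded 7 or 9 whose ventilation or ICU care had ended keep their completed count.
4. Keep hospital days as recorded as the primary comparison for that outcome, labelled index-hospital days. Add a sensitivity analysis that treats codes 7 and 9, and deaths, as stays not completed.
5. Fix the rule before transfers by arm are known.

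The cost is a paragraph of plan wording and a short status entry at discharge. The rank test is already named in Statistical Considerations, though not for Aim 3. The downside is that ventilator and ICU effects are reported on ranks rather than as mean days, and worst ranking is a conservative assumption about the patients it applies to.

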Collecting and analyzing data on weight-bearing lower extremity exercise in this patient population will allow us to obtain important information on ways to address weakness associated with ECMO treatment, particularly in those who are unable to engage in bipedal ambulation.

[figure not shown]
MOVEO XP Mobile Hi-Lo Platform System

Company Website:

<http://www.djoglobal.com/products/charlottesville/moveo-xp>

ECMO Early Mobilization Protocol:

1. **Readiness for Mobility Assessment and Protocol** (Developed by ECMO therapy specialists at the University of Minnesota Medical Center)
 - a. Passive range of motion (PROM) and monitor for appropriateness of entering into the mobility program
 - b. Utilization of lift equipment to sit patient at the edge of the bed or into chair to promote wakefulness, when on minimal amounts or no sedation
 - c. Patient demonstrates the ability to follow 3/3 one-step commands
 - d. Patient tolerates 5 minutes of lower extremity ergometer, or performs ten reps of 3 active ROM of motion exercises involving the lower extremities
 - e. Sit at bedside unsupported for 5 minutes
 - f. Sit->stand and pre-gait activities (weight shifting, walking in place, etc.) directed by therapist
 - g. Bed->chair transfers (stand-pivot or squat-pivot)
 - h. Walking over ground with utilization of the mobility carts

The primary aim of this study is to assess the functional impact of leg exercise during the pre-ambulation phase in patients undergoing ECMO. Outcome measures will be categorized as either functional or hospital based. Hospital measures include: Hospital days, intensive care unit days, days on ECMO, days on mechanical ventilation, length of time from physical therapy evaluation to initial ambulation, and discharge disposition. Functional outcome measures include: Leg strength, grip strength, 30-second sit to stand test, Functional Status Score for the Intensive Care Unit (FSS-ICU), and the Richmond Agitation and Sedation Scale (RASS).

Background & Significance

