Aim 1: To determine if closed-chain leg exercise decreases the time to initial ambulation. *We hypothesize* that adding leg exercise will decrease time to ambulation.

Aim 2: To determine the impact of closed chain leg exercise on functional ability. *We hypothesize* that adding leg exercise will improve functional outcomes when added to an existing early mobilization program.

Aim 3: To determine the effect of closed chain leg exercise on hospital outcomes. *We hypothesize* that hospital related outcomes will improve when leg exercise is added to an existing early mobilization program.

Research Design & Methods

This initial pilot study will be conducted at the University of Minnesota Medical Center (UMMC), Fairview, and will involve 10 participants in each of the two groups (A and B). To account for attrition, 24 total subjects will be recruited; 12 per group. Approximately 3-5 patients are admitted to UMMC each month who are undergoing ECMO and could be considered for study inclusion. The study will be conducted with a goal endpoint of 1-year. Men and women aged 18-70 years old with refractory respiratory failure who are undergoing ECMO will participate over the duration of their ECMO treatment and hospitalization.

Recruitment and Consent

Standard practice includes a physician order for inpatient physical therapy for all individuals undergoing ECMO, as well as initial medical sedation. Most of those receiving ECMO are at least partially medically sedated at the time of physical therapy initiation. Only physical therapists who are specialty-trained ICU therapists and who are a part of this project will be working with this group of patients.

Any individual who meets inclusion criteria will be considered for participation, pending their ability to follow 3/3 one-step commands, as is outlined in the ECMO Mobility Protocol listed previously. Patients will be able to self-consent once sedation is reduced. After consent, individuals will be placed into either Group A or B and progress through the protocol. Group assignments will be determined based on 24 subjects, with the number 24 put into a random letter sequence generator prior to subject recruitment.

Inclusion Criteria

- Men and women 18-70 years old with refractory respiratory failure undergoing ECMO at the University of Minnesota Medical Center, Fairview.
- Able to follow 3 out of 3 one-step commands via protocol.
- Active Inpatient Physical Therapy Referral.

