- ECMO delivery is veno-venous with internal jugular catheter.

Exclusion Criteria

- Femoral catheter of any kind present.
- Veno-arterial ECMO setup.
- Sedation such that self-consent is not attainable.
- Medical instability, as determined by primary critical care physician.

Overview of Protocol for Aims 1-3:

Participants in either Group A (closed chain leg exercise group) or B (open chain exercise group) will progress through the established ECMO protocol led by their physical therapist. Participating therapists have extensive experience in working with patients on the Moveo who are in the ICU. Subjects will be assisted in the supine position from their bed to the Moveo device via a lateral transfer across a slide board to facilitate ease of movement.

Those in Group A will participate in leg exercise on the Moveo during item 4d of the ECMO protocol, whereby those in Group B will complete standard exercise as listed in item 4d. Group A participants will use the Moveo until subjective report of leg fatigue. Participants will self-select the pace of their leg exercise and the primary therapist will determine guidelines for percent of body weight lifted in accordance with standard practice physical therapy. Subjects will complete 1-4 sets of up to 25 reps of the squat exercise with 2 minutes of rest between each set. Subjects will receive physical therapy 5 days/week regardless of randomization into Group A or Group B.

Data Collection for Aims 1-3: Data will be collected on Day 0 (physical therapy evaluation day), Day 5, Day 10, Day 15, Day 20, Day 30, Day 45 (if applicable), and Day of discharge. Data collected will be categorized as specific to Aim 1 (time from initial physical therapy evaluation to initial ambulation), Aim 2 (functional outcomes) and Aim 3 (hospital outcomes). Recording of physiological data including heart rate (HR), blood pressure (BP), oxygen saturation (O2), and respiratory rate (RR) will be completed by trained physical therapists involved in the protocol at the onset of, and 1-minute post-conclusion of each therapy session. Therapy sessions are to be delivered at a frequency of five sessions per week.

- Functional Outcomes

- Leg strength as assessed by primary therapist via manual muscle test, using the Medical Research Council Sum Score (MRC Score)
- Grip strength, as assessed by hand dynamometer, completed by primary therapist

- 30-second sit to stand, completed by primary therapist

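### A per-day comparison rule conflicts with the plan's own aim-specific tests, and no single primary outcome or time point is fixed

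*Combined protocol and SAP*

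**What the plan says.** All references are to the Project Proposal within the combined protocol and SAP.

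- **Per-day rule.** Statistical Considerations says "Functional and Hospital outcomes will be analyzed to compare group differences at each of the data collection days". The schedule under Data Collection for Aims 1-3 reads "Data will be collected on Day 0 (physical therapy evaluation day), Day 5, Day 10, Day 15, Day 20, Day 30, Day 45", with Day 45 only where applicable, plus the day of discharge. That makes eight occasions.
- **Aim-specific tests.** Later in Statistical Considerations, Aim 1 gets one t-test and Aim 2 gets repeated measures ANOVA for group and time. Aim 3 gets one t-test per hospital outcome, with a chi-square test for discharge disposition.
- **Outcomes.** Five are functional: leg strength, grip strength, 30-second sit to stand, FSS-ICU and RASS. Six are hospital-based: hospital, ICU, ECMO and ventilation days, time to ambulation, and disposition.
- **Primary aim.** The outcome paragraph after the ECMO Early Mobilization Protocol says "The primary aim of this study is to assess the functional impact of leg exercise". Specific Aims puts a different question first, as Aim 1: "To determine if closed-chain leg exercise decreases the time to initial ambulation". The variable for Aim 1 also appears in the hospital list: "Length of time from physical therapy evaluation to initial ambulation".
- **Not stated.** The document gives no alpha, sidedness, primary outcome, primary time point or ranking of outcomes.

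**The concern.** The per-day sentence and the aim-specific list describe different analyses. For functional outcomes, one route compares the groups separately on each day and the other fits a single longitudinal model. For hospital outcomes the per-day rule cannot work as written, at least for hospital days, ICU days and disposition, because each patient has only one final value.

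Nothing says which result would count as the answer. All three aims carry directional hypotheses of benefit. With no outcome or time point singled out, a chance difference on one measure on one day could be reported as confirming an aim. It could also steer the choice of endpoint for a follow-on trial.

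**Working it through.** The plan states no alpha, power or error rate, so there is no figure of its own to reproduce. The check counts the tests under each reading and works out the chance of at least one p < 0.05 when there is no effect.

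**Inputs from the document:** 5 functional outcomes, 6 hospital outcomes, 8 collection occasions (7 after Day 0), 10 analysed patients per group.

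**Assumptions:** alpha 0.05 two-sided per test, unadjusted. Day 0 is left out because it is the evaluation day, and a difference then would not be read as an exercise effect. Each hospital outcome is counted once, including time to ambulation.

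**Formula for k independent tests:** P(at least one) = 1 − 0.95^k; expected false positives = 0.05 × k.

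| Reading | k | P(at least one) |
|---|---|---|
| One test per outcome | 5 + 6 = 11 | 1 − 0.95^11 = 43.1% |
| Aim-specific plan, with group and group-by-time effects both read for each functional outcome | 5 × 2 + 6 = 16 | 1 − 0.95^16 = 56.0% |
| Per-day rule without Day 45 | 5 × 6 + 6 = 36 | 1 − 0.95^36 = 84.2% |
| Per-day rule | 5 × 7 + 6 = 41 | 1 − 0.95^41 = 87.8% |

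At 41 tests the expected number of false positives is 0.05 × 41 = 2.05.

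**Allowing for correlation.** These outcomes are correlated with each other and over time, so independence gives the upper end. Null trials were simulated with 10 per group and two-sample t-tests, since the groups are different patients. The correlations are assumed.

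- *41 tests.* Correlation between outcomes ran from 0 to 0.7 and autoregressive day-to-day correlation from 0 to 0.9, with the functional and hospital blocks independent of each other. The chance of at least one false positive ran from 88% down to 50%. In the middle of the grid (0.5 between outcomes, 0.7 day to day) it was 72%.
- *41 tests, all equally correlated.* 76% at 0.3, 59% at 0.5 and 40% at 0.7.
- *11 tests.* 29% to 43% with the blocks independent, and 23% to 43% if all 11 are equally correlated at 0 to 0.7.

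The simulation assumes complete data at every visit, although patients discharged early will not contribute to later days. The physiological comparisons (heart rate, blood pressure, oxygen saturation, respiratory rate) are not counted and would add tests.

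**The case against.** The strongest reply is that the per-day sentence names no test. It can be read as describing the visit schedule, with the tests given under the aims. On that reading Aim 3 already compares each hospital outcome once and Aim 2 already has a longitudinal model. The study is also an exploratory pilot with no power claim, for which formal error control is not normally expected.

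Much of this stands. The size of the problem depends on the reading: with one test per outcome, a chance finding is less likely than not. But the sentence does say that groups will be compared on each day, and nothing subordinates it to the aim list. Nor does the aim list say which ANOVA effect answers Aim 2. Pilot status removes the need for alpha correction. It does not remove the need to say which result answers the question when the hypotheses are directional.

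Three stronger readings are tempting, and the document does not support them:

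- **Two primary aims.** Only functional impact is called primary. Time to ambulation is listed first but not so labelled. The two primary factors mentioned under Aim 2 are group and time.
- **Eighty-eight tests (11 outcomes × 8 days).** Hospital totals and disposition do not yield a fresh result on every day, and Day 0 is baseline.
- **Extra false-positive risk from listing time to ambulation under both Aim 1 and Aim 3.** It is the same test and the same p-value. It should be listed once for clarity only.

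**Conclusion.** The concern holds in this form: the per-day rule contradicts the plan's own tests, and neither the labelled primary aim nor Aim 1 settles one primary outcome and time point for the study. If the per-day rule is followed, at least one chance finding is more likely than not under most of the correlations tried (about 50% to 88% over 41 tests). It falls below half only when correlation is very strong. With one test per outcome the figure is at most about 43%.

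These figures rest on an assumed alpha of 0.05, assumed correlations and complete follow-up. The conflict within the text needs none of those assumptions. It should be corrected before analysis. The consequence is moderated by the pilot status.

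**What to change.** 1. Delete the per-day comparison sentence from Statistical Considerations.
2. Test each functional outcome once, through one pre-specified group contrast from the Aim 2 repeated-measures model, stating the effect or time point it refers to. Test each hospital outcome once.
3. List time to ambulation under Aim 1 only.
4. Name one primary outcome, state alpha, and align the primary-aim sentence with Specific Aims. Time to initial ambulation is the natural candidate because it already has its own hypothesis and single test. If the sponsor keeps functional impact as primary, it should name one functional measure and one contrast.
5. Label all other outcomes and all per-day differences exploratory. Report them as estimates with 95% confidence intervals and no significance claim.

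With one primary test, the chance of a false claim on the deciding result is 5% at the assumed alpha, and no multiplicity adjustment is required. The cost is a few sentences, with no additional patients, data or procedures. The downside is that isolated per-day or secondary p-values can no longer be presented as confirming an aim.

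### Functional comparisons at late fixed days and at day of discharge depend on length of stay, itself an outcome, so a real benefit can be attenuated by an unknown amount

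*Combined protocol and SAP*

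**What the plan says.** The Statistical Considerations section of the project proposal analyses functional and hospital outcomes to "compare group differences at each of the data collection days (0, 5, 10, 15, 20, 30, 45, day of discharge". For Aim 2 it names group and time as the two factors and adds: "To assess both factors, repeated measures ANOVA will be used".

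The schedule under Data Collection for Aims 1-3 ends with "Day 20, Day 30, Day 45 (if applicable), and Day of discharge". Only Day 45 carries a qualifier. Under Research Design & Methods, patients "will participate over the duration of their ECMO treatment and hospitalization", and no assessment after discharge is described.

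"Hospital days" is a listed hospital outcome. The Aim 3 hypothesis is that "hospital related outcomes will improve when leg exercise is added to an existing early mobilization program", which for length of stay means a shorter one.

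The plan gives no primary time point for Aim 2 and no rule for a patient who is discharged, is transferred or dies before a scheduled day. The one sentence on incomplete data, under Stopping Rules, concerns withdrawal.

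**The concern.** Whether a patient has a Day 20, 30 or 45 score depends on still being in hospital, which is decided after randomisation and which the trial hopes to change. If Moveo speeds recovery and recovered patients leave sooner, Group A's late-day scores come from its slower patients, set against a Group B that has lost fewer of its better ones. Randomisation does not protect that contrast.

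Day of discharge has a related problem. It is not a common time point: one patient may reach it on Day 12 and another on Day 50. If function influences when patients leave, both groups are measured near a similar exit level, and the benefit appears in the timing rather than in the score.

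At stake is the reading of Aim 2. It could report little functional benefit partly because patients left earlier, so that Aims 2 and 3 seem to disagree. Enrolling more patients would not remove the distortion, and a pilot estimate distorted in this way would mislead the design of a later trial.

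**Working it through.** **Inputs from the documents.** Comparison days 0, 5, 10, 15, 20, 30, 45 and discharge; in-hospital follow-up only; the study "will involve 10 participants in each of the two groups (A and B", with 12 per group recruited to allow for attrition. That step is consistent with attrition up to 16.7%, since 10 / (1 − 0.167) = 12. No length of stay, SD, effect size or discharge rule is given, so there is no plan figure to reproduce on this point and everything below is assumed.

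**Model 1, short stays.** Score = b + g × day, with b of mean 10 and SD 3, and g of median 0.7 points per day with log-SD 0.5. Group A gains 30% faster. Discharge comes when the score reaches about 25 (threshold SD 0 or 3).

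- Approximate median stay: (25 − 10) / 0.7 = 21.4 days in Group B and 21.4 / 1.3 = 16.5 days in Group A.
- True mean difference per day: 0.3 × 0.7 × exp(0.5² / 2) = 0.3 × 0.7 × 1.133 = 0.238 points. That is 2.4 points at Day 10 and 4.8 at Day 20. With a score ceiling of 35 the simulated differences are 2.3 and 3.0.
- Day 20, patients still in hospital: difference 0.8 to 1.1 points, with about 35% of Group A and 53% of Group B remaining. With the ceiling this is roughly 25 to 35% of the true difference. Without it, 0.8 / 4.7 to 1.0 / 4.7, or 17 to 21%.
- Day of discharge: everyone leaves near 25, so the difference is about 0.

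This model lets function alone decide discharge. With the ceiling of 35 and that influence halved, Day 20 keeps about 69%; with discharge unrelated to function it keeps 100%.

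**Model 2, influence of function varied.** Log discharge time = w × log(time to reach a functional threshold) + (1 − w) × log(unrelated medical time). Group A recovers 40% faster, median stay is about 30 days, and there are 400,000 simulated patients per arm. Entries are the in-hospital difference as a share of the true difference on that day. The last column is the discharge-day difference as a share of the true difference at the median stay.

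| w | Day 10 | Day 20 | Day 30 | Day 45 | Discharge |
|---|---|---|---|---|---|
| 0 | 100% | 100% | 100% | 101% | 113% |
| 0.25 | 99% | 92% | 85% | 78% | 73% |
| 0.5 | 96% | 69% | 51% | 39% | 44% |
| 0.75 | 85% | 43% | 22% | 11% | 20% |
| 1 | 67% | 30% | 15% | 7% | 0% |

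With a median stay of 45 days, Day 20 keeps 59 to 100%. With a median of 20 days, Day 10 keeps 41 to 100%. At a median of 30 days, the expected number still in hospital at Day 45, out of 12, is 0.5 to 2.5 in Group A and 1.4 to 2.5 in Group B.

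**Check of the remedy.** In Model 1, with the influence of function varied and with or without the ceiling, Day 10 keeps from about half to all of the true difference among in-hospital patients only. Using the discharge score for those who have left, it keeps 71 to 99%. The remaining loss arises because a score frozen at discharge misses later gains, and more of Group A has left by then.

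Deaths and transfers were not simulated.

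**The case against.** A reader might infer that a real Moveo benefit will be largely hidden, and that the bias always runs against the trial's hypothesis and grows with each later day. The documents do not support that. Nothing in them says function sets discharge. The nine disposition categories include five care settings and three forms of home with help or therapy, which does not fit everyone leaving at one good score. If discharge is unrelated to function, nothing is lost. Losing the sickest patients to death, or moving poorly functioning patients to facilities, could push the bias either way. Stays of 16 to 22 days are also assumed; a schedule running to Day 45 suggests that longer stays were expected. These objections stand, and they limit the claim to possible attenuation of unknown size.

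A second objection is that a longitudinal model using every available value, with discharge scores placed at their actual day, would recover much of the difference. In a rerun of Model 1 without the ceiling, a random-slope mixed model recovered 3.7 to 4.1 of 4.7 points at Day 20. That is true of such a model, but the plan names a repeated measures ANOVA and separate by-day comparisons. Keeping every available value does not repair the by-day and discharge contrasts.

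A third is that this is a pilot. Days 5, 10 and 15 are also compared, Aims 1 and 3 could still show a benefit, and power is low in any case. At 12 per group and two-sided 0.05 (assumed), power for 0.54 SD is Φ(0.54 × √6 − 1.96) = Φ(−0.64), about 26%. Low power is a separate limitation; it does not justify a contrast selected on an outcome.

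**Conclusion.** The concern holds in limited form. As written, the plan compares function between groups in patients selected by a post-randomisation outcome that the trial expects to change, and it treats a patient-specific day as if it were a common time point. No other rule in the documents corrects this.

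To the extent that better function leads to earlier discharge, a real benefit is attenuated at late days and at discharge, possibly severely. The size cannot be determined from the documents. Under the assumed inputs, Day 20 keeps from under a third to all of the true difference, and the discharge-day comparison anywhere from none to all of it. These ranges rest on linear recovery, assumed lengths of stay and no deaths or transfers. The change is worth making because it improves the Aim 2 comparison without new data.

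**What to change.** - Name Day 10 as the main between-group comparison of function for Aim 2.
- For patients discharged before Day 10, use the discharge-day score that is already collected.
- Rank deaths lowest and use the rank-sum test for this comparison; the plan already lists that test for non-parametric data. Do not apply the death rule to RASS, where a lowest rank has no clear meaning.
- Remove day of discharge as a level of the repeated measures ANOVA and as a between-group test of function.
- Report day of discharge and Days 20 to 45 descriptively, with the number still in hospital and the median discharge day in each arm.

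Day 5 should not stand in for Day 10, even if early discharge proves common. Day 0 is the physical therapy evaluation, when most patients are still at least partly sedated; consent, group placement and Moveo come later. Day 5 may therefore precede meaningful exposure. The same delay affects Day 10 less, to an extent the documents do not give.

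The cost is plan wording only. Late-day results become descriptive, which narrows what Aim 2 can test across time. Using the discharge score still loses some of the difference, up to about 30% at Day 10 if function alone sets discharge (1.7 of 2.4 points, or 71%, retained).
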